Aim 1: A sample size of 80 participants receiving 3 randomized messages per day for 30 days will provide 7,200 observations. Across person-days, there will be an average of one prompt per day for each of the 3 conditions CBT, Mindfulness/ACT, and control (balance across person-days). Power estimations were conducted using an online tool specifically developed for sample size calculations for micro-randomized trials by consultant [name]. Assuming a message randomization probability of 1/3 (33% CBT, 33% Mindfulness/ACT, 33% control), a quadratic effect over time (initially smaller as participants are getting used to the intervention, increasing over time to peak at day 20, and decreasing thereafter as participants may get desensitized), and an average compliance rate of 75%, linearly decreasing over time, a sample size of N=80 participants will allow for detecting a standardized mean difference between CBT, Mindfulness/ACT, and control conditions on the primary outcome self-reported smoking urge of $d=0.1$ with a power of 0.8 and an alpha level of 0.05. This measure of effect size is a generalization of Cohen's d (standardized mean difference), with the difference that the standardization is by the average standard error over the entire study, with multiple treatments for each person. A Cohen's d of 0.1 is considered a small effect. A previous EMA study found that playing Tetris (analogous to a CBT distraction technique) decreased substance use urges with a mean effect size of $f^2=0.12$ (medium sized effect). Given these effect sizes in the existing literature, we will be adequately powered to detect effects in Aim 1 analyses.

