After informed consent has been obtained, participants will be asked for the contact information (email address and phone number) so that the study team can stay in contact. Final enrollment of a participant will depend on identity verification. Since data collection for this study will take place remotely, participants will be required to submit a picture of an official ID document for verification of their identity and age, a procedure that [name] has found to be feasible in his previous studies. After verification of identity, participants will be enrolled into the study. Only the participant picture on the ID (headshot) will be retained for biochemical verification of smoking abstinence. The ID document will subsequently be deleted after validation of participant details for enrollment.

Baseline survey: Initially, all participants will complete a baseline survey on the online survey platform Qualtrics, to assess basic demographics, smoking and other tobacco use behavior, including e-cigarettes, nicotine dependence, quitting history and current quit motivation, frequency and intensity of smoking urges, and other substance use behavior including alcohol, cannabis, and other illicit drugs. Smoking-specific experiential avoidance, a measure to assess a person's willingness to experience negative mental states (e.g., urges, mood, thoughts), will be assessed with the Avoidance and Inflexibility Scale. Trait mindfulness will be assessed with the FIT-60 (Flexibility Index Test).¹⁴³ Baseline measures will also include trait negative affect and psychological distress.

EMA data collection: Before EMA data collections, participants will be contacted on the phone to receive detailed instructions on how to use the EMA study app. Participants will use their own smartphones and the study app to collect data on smoking situations over the course of 14 days (EMAs of smoking situations and smartphone location sensor data). Participants will complete 3 randomly prompted EMA surveys per day and will report every time they smoke a cigarette. A random subset of these cigarette reports will trigger up to 3 EMA smoking survey prompts per day.

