EMA momentary surveys: Smoking urges will be recorded with a single item in accordance with recommendations from the Society for Research on Nicotine and Tobacco. Additional questions will examine internal and external aspects of the situation. The number of questions asked will be limited to ensure they do not interfere with participants' daily activities. In addition, the EMA software will log participants geolocation based on GPS. All data will be time and date-stamped to allow time-specific analyses and determine high-risk periods for smoking.

EMA daily diaries: Thorough daily diaries will be collected to assess overall cigarettes, other tobacco product (including e-cigarettes), alcohol, cannabis, and other substance use (illegal drugs). Questions will also assess same occasion co-use of tobacco, alcohol, cannabis, and drugs (when participants were feeling under the influence of other substance).

Purpose of the EMA training phase: The EMA training phase serves multiple purposes: First, it allows participants to get used to the study app that will also deliver the intervention messages, and second, the collected data will allow us to generate an individual risk profile with regard to time of day and location (by combining timestamps, GPS data, and self-reported data) with the highest likelihood of smoking for each participant. We will use geofencing to generate geospatial buffers around these high-risk locations. In combination with time of day information to target high-risk time periods for smoking, these geofences will trigger delivery of intervention messages when a mobile device enters the area: A message can be triggered when a participant approaches a smoking location during one of the high-risk time windows. We will use our established protocol for triggering intervention messages that we have successfully used in a pilot trial.

Intervention phase - Micro-randomized trial with N=80 participants to determine message efficacy

The micro-randomized trial will determine if CBT and Mindfulness/ACT messages are superior to control messages in reducing the primary outcome momentary smoking urges. Based on participants' training

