Analyses for message acceptability testing will utilize a mixed methods approach. For the quantitative analyses, the **primary outcome** will be message acceptability expressed as the average score of Likert responses to helpfulness to cope with smoking urges or craving and to support quit attempts and acceptability of message content and design. Messages will be ranked by score and messages with low scores will be either modified in line with qualitative participant feedback or removed before moving to the next study phase. Analyses assessing message acceptability across age, gender, and race/ethnicity will include independent variables age, gender, race/ethnicity, educational attainment, psychological flexibility, smoking frequency, quit motivation, and past quitting attempts. These quantitative analyses on message acceptability will be supplemented with qualitative analyses involving inductive and deductive coding of participants' open-ended responses to inform how messages should be modified.

Analytical strategy Aim 1: To compare CBT and ACT intervention message efficacy.

Aim 1 analyses to test the hypothesis of a proximal benefit of urge reduction messages will be conducted using a centered and weighted least squares method, which estimates treatment effects and allows inclusion of covariates. The method is similar to GEE and multi-level models in that it accounts for dependence of responses within individuals due to repeated measures via the use of robust standard errors. Moreover, the method takes advantage of the sequential randomization to estimate causal treatment effects. The **primary outcome** will be participants' rating of **smoking urge** in EMA-post surveys, prompted 15 minutes after intervention message delivery, and controlling for the ratings in EMA-pre surveys. The main independent variable will be message type: **CBT versus Mindfulness/ACT versus a Control Message** ("Thank you for completing the survey"). We will also **test differences in efficacy between CBT versus Mindfulness/ACT**. We will use **multiple imputation** to impute missing data in EMA-post surveys.

Analytical strategy Aim 2: To test if urge reduction messages change smoking behavior over time.

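### The Aim 1 primary model pre-specifies only the EMA-pre urge rating as a covariate and leaves the training-phase urge ratings unused, giving up a little free precision

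*Combined protocol and SAP*

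**What the plan says.** **Model.** Section V.C.4 (Analytical strategy Aim 1) takes EMA-post urge as the primary outcome, "prompted 15 minutes after intervention message delivery, and controlling for the ratings in EMA-pre surveys". It says that the method can take covariates and that robust standard errors deal with dependence within a person. It names no covariate beyond the EMA-pre rating. The Aim 2 strategy in the same section, by contrast, lists gender and nicotine dependence.

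**Training data.** Section V.C.1 describes a 14-day training phase before any message: "Participants will complete 3 randomly prompted EMA surveys per day and will report every time they smoke a cigarette". A subset of cigarette reports triggers up to three further surveys a day. For the momentary surveys, "Smoking urges will be recorded with a single item in accordance with recommendations from the Society for Research on Nicotine and Tobacco". The stated purposes of this phase are to familiarize participants with the app and to build the time and location risk profile behind the geofences. The documents do not bring training-phase urge into the Aim 1 model.

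**Power.** Section III.B states: "A sample size of 80 participants receiving 3 randomized messages per day for 30 days will provide 7,200 observations". It assumes equal allocation to three message types and "an average compliance rate of 75%, linearly decreasing over time". The target is a difference "on the primary outcome self-reported smoking urge of $d=0.1$ with a power of 0.8 and an alpha level of 0.05".

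**The concern.** Robust standard errors make the inference valid when ratings cluster within people. They do not take stable differences between people out of the residual; only a covariate, or differencing, does that. Message type is drawn separately at each prompt and no balancing within a person is described, so those stable differences add noise to every message contrast. One momentary EMA-pre rating captures a person's usual urge level only in part. The mean of about 30 earlier ratings captures it much better.

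What is at stake is the width of the confidence intervals for the Aim 1 contrasts, including CBT against Mindfulness/ACT, in a trial aimed at a small effect. A covariate chosen after outcomes are seen is open to criticism, so the time to name it is now.

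**Working it through.** **1. The plan's own power figure.** Inputs from section III.B: N = 80, 90 prompts per person, allocation 1/3, average compliance 75%, d = 0.1, alpha 0.05, and a quadratic effect, "initially smaller as participants are getting used to the intervention, increasing over time to peak at day 20". The initial effect and the compliance slope are not given. I used an F test on 3 and 74 degrees of freedom, with noncentrality = 80 × Σ over 90 prompts of compliance × (1/3)(2/3) × d(t)².

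- Initial effect 0, flat compliance: noncentrality 13.79, power 0.87.
- Initial effect 0.08, compliance falling from 95% to 55%: noncentrality 11.86, power 0.81.

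The stated 0.80 is therefore reproduced to within tolerance (0.81-0.87) without the extra covariate. This calculation sets one message type against the other two pooled; whether that is the right contrast is a separate matter. A simple pairwise z test has 80 × 90 × 0.75 / 3 = 1,800 prompts per type, z = 0.1 × √(1800/2) = 3.0, and power Φ(3.0 − 1.96) = 0.85.

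**2. Effect of the extra covariate.** Set total urge variance to 1. Let ICC be the between-person share, r the within-person correlation of EMA-pre with EMA-post, ρ the correlation of a person's training-phase level with their level at message prompts, and m the number of training ratings. The documents give none of ICC, r or ρ; I assume 0.3-0.5, 0.3-0.9 and 0.6-1.0. For m I take 75% of 3 × 14 = 42, which is 31.5 (75% is stated for the message phase and assumed here).

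- Correlation of pre with post: c = ICC + (1 − ICC)r
- Residual variance given EMA-pre: V0 = 1 − c²
- Covariance of the training mean with either rating: k = ρ × ICC
- Variance of the training mean: v = ICC + (1 − ICC)/m
- Residual variance given both: V1 = V0 − k²(1 − c)²/(v − k²)
- Proportional cut: q = 1 − V1/V0

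Middle case (ICC 0.4, r 0.5, ρ 0.8): c = 0.70, V0 = 0.510, k = 0.32, v = 0.419. Then V1 = 0.510 − 0.00922/0.3167 = 0.481 and q = 5.7%.

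| ICC, r | V0 | q, ρ = 1.0 | q, ρ = 0.8 | q, ρ = 0.6 |
|---|---|---|---|---|
| 0.3, 0.7 | 0.376 | 4.5% | 2.6% | 1.3% |
| 0.4, 0.5 | 0.510 | 10.9% | 5.7% | 2.8% |
| 0.5, 0.3 | 0.578 | 19.9% | 9.5% | 4.5% |
| 0.3, 0.9 | 0.135 | 1.4% | 0.8% | 0.4% |
| 0.4, 0.9 | 0.116 | 1.9% | 1.0% | 0.5% |
| 0.5, 0.9 | 0.098 | 2.4% | 1.2% | 0.5% |

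Adding the smoking-triggered surveys (about 63 ratings in all) barely changes this: at ICC 0.4, r 0.5, ρ 0.8 the cut goes from 5.7% to 5.9%.

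**3. Does the residual cut reach the contrast?** The model was simulated with 80 people, 90 prompts, 75% observed and person-clustered robust standard errors, 1,500 runs per setting. Variance cuts, empirical then robust, were:

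- ICC 0.4, r 0.5, ρ 1.0: 12% and 11%
- ICC 0.5, r 0.3, ρ 1.0: 22% and 19%
- ICC 0.4, r 0.5, ρ 0.7: 3% and 4%
- ICC 0.4, r 0.8, ρ 0.8: 1% and 2%

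Estimates were unbiased with and without the covariate.

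**4. Power and equivalent sample size.** From a start of 0.80, power = Φ((1.960 + 0.842)/√(1 − q) − 1.960), and the equivalent N is 80/(1 − q).

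- q = 1%: power 0.804, N about 81
- q = 5.7%: power 0.823, N about 85
- q = 20%: power 0.879, N = 100

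**The case against.** The strongest reply is that nothing in the plan is wrong. The model already adjusts for the most proximal measure of the outcome, inference is valid, and one more prognostic covariate is an efficiency preference. That stands, and it limits the point to an optional improvement.

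The size is also open to challenge. A reader might infer that the plan throws away 5-20% of the variance. That range needs a person's training-phase urge level to equal their level at message prompts. The documents give reason for doubt: training ratings come from random prompts, message prompts are triggered at individually high-risk places and times, and participants plan to quit within 30 days, so levels may shift between phases. The 20% figure also needs a correlation of only 0.3 between two ratings of the same item about 15 minutes apart. With a high pre-post correlation or a weaker link between phases, the gain falls to a few percent or less.

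A reader might also infer that other covariates are ruled out. The text does not say so. It answers a form item asking for a brief plan and notes that the method accepts covariates; what can be said is that none beyond EMA-pre is pre-specified.

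Finally, the power gains depend on scaling. Section III.B does not say whether d is standardized before or after EMA-pre adjustment, and a pairwise test that starts at 0.85 has less to gain.

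What survives is that the covariate precedes every message randomization, adds no bias, does not raise large-sample variance, and uses data already collected.

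**Conclusion.** The point holds as a free improvement, not as an error. The Aim 1 model pre-specifies one covariate and leaves the training-phase urge ratings unused. Under the assumed ranges (ICC 0.3-0.5, pre-post correlation 0.3-0.9, cross-phase correlation 0.6-1.0) the variance of the message contrast would fall by roughly 1-20%; the least favorable corner gives 0.4% and the middle case about 6%. A contrast with power 0.80 would rise to about 0.80-0.88, provided d = 0.1 refers to the residual after EMA-pre adjustment.

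The documents do not support a reading that the primary analysis is biased, or that leaving this covariate out makes the trial underpowered. Severity is optional. Confidence is high that the covariate is available and harmless, but only moderate on the size of the gain.

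**What to change.** In section V.C.4, Analytical strategy Aim 1, add two or three sentences:

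- Name each participant's mean urge at random prompts in the 14-day training phase as a second control covariate, beside the EMA-pre rating, in the primary model.
- Include it in the multiple imputation model for missing EMA-post ratings, so that the imputation and analysis models agree.
- Give a simple rule, fixed before outcomes are seen, for participants with few or no training ratings: a minimum number of ratings, and what replaces the mean below it.

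The cost is a short wording change and one extra parameter with 80 participants. It needs no new data and adds no prompts or participant burden. It would also help for section III.B to state whether d is standardized before or after covariate adjustment.

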Testing the Impact of Smartphone-based Messaging to Support Young Adult Smoking Cessation - Pilot

NCT05991934

3/19/25

JHSPH IRB Research Plan for New Data Collection

Use this template for new data collection and if you also will analyze secondary data. Answer the questions below and for numbered sections that do not pertain to your study, retain the section numbers and bolded questions, and write "N/A". Please start typing in the gray boxes provided.

PI Name: [name]

Study Title: Testing the impact of smartphone-based messaging to support young adult smoking cessation

IRB No.: IRB00013413

PI Version No. / Date: V7, 03/19/2025

I. Aims of the Study: Describe the aims/objectives of the research and/or the project's research questions or hypotheses.

Clinical practice guidelines for smoking cessation emphasize cognitive behavioral therapy (CBT) to help patients develop coping strategies for urges. Mindfulness or Acceptance and Commitment Therapy (ACT) offer a different approach, which teaches smokers psychological flexibility through accepting negative experiences. While there is evidence for the efficacy of both CBT and Mindfulness/ACT smoking cessation interventions, it is unclear if these approaches are efficacious when implemented in real-time and with young adults. The overall goal of this proposal is to evaluate the efficacy of CBT and Mindfulness/ACT messages for young adults targeted at specific high-risk situations for smoking.

This research will address the following specific aims:

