Aim 1: To test CBT and Mindfulness/ACT intervention message efficacy for reducing momentary smoking urges (N=80). To inform just-in-time interventions, it is crucial to test if CBT and Mindfulness/ACT based messages can reduce momentary smoking urges. We will conduct a micro-randomized trial (repeated within-subject randomizations of messages) to accomplish this. In line with our existing protocol, participants first collect EMA data for 14 days, allowing us to determine high-risk situations for smoking. In the following intervention phase, participants receive tailored messages triggered by geofencing of participants' high-risk locations for a total of 30 days. Tailoring is based on established predictors of smoking relapse (stress and presence of other smokers). The micro-randomized trial tests the efficacy of CBT versus Mindfulness/ACT versus control messages for reducing smoking urge 15 minutes post message delivery. Secondary outcomes include smoking or other tobacco use (including e-cigarettes), affect, and stress.

Aim 2: To test if exposure to urge reduction messages results in changes in smoking behavior over time compared to an EMA only control group (N=80). It is important to investigate if repeated messages in the micro-randomized trial impact smoking behavior over time, in contrast to just repeated assessment without messages. Thus, this study includes a conventionally randomized clinical-trial component. Parallel to the micro-randomized trial group, a control group completes EMA surveys only without intervention messages. This allows us to test if messages reduce smoking behavior. The primary outcome is number of cigarettes per day at end of treatment, 3-, and 6-months follow-up. Secondary analyses explore biochemically verified 7-day point prevalence abstinence, switching to e-cigarettes, and other tobacco outcomes. Post-hoc dose-response analyses investigate the long-term efficacy of CBT or Mindfulness/ACT messages on smoking behavior.

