Aim 2: This aim will test between group differences in number of cigarettes smoked over time among micro-randomized trial (N=80) and EMA-only control group participants (N=80). Sample size calculations were based on findings from a recent app-based mindfulness meditation trial for smoking reduction. This trial only delivered intervention content for 14 days (as opposed to the 30 days proposed here) and found a significant reduction in 3.8 cigarettes/day in the intervention group compared to an increase in 0.8 cigarettes/day in the control group, which translates to an effect size of $d=0.651$ ($f=0.326$). Power estimation for between group repeated measures ANOVA and interactions were conducted with G-Power. Assuming an alpha level of 0.05, a sample size of N=160 will allow us to detect effects in reduction of cigarettes per day of $f=0.326$ and larger with a power of 0.80. Multiple imputation will be used for missing data and the full sample will be analyzed.

IV. Participants:

Describe the study participants and the population from which they will be drawn. Specify the inclusion and exclusion criteria. If you plan to include children, note their ages and whether you will include children in foster care. Note if the participants are particularly vulnerable in terms of cognitive limitations, education, legal migration status, incarceration, poverty, or some combination of factors.

A. Inclusion Criteria:

Participants will be young adult men and women who: 1) live in the U.S.; 2) read English; 3) are between 18 and 30 years of age; 4) own a smartphone with iOS and Android operating system and GPS capabilities; 5) are carrying their smartphone with them every day; 6) are willing to participate in the study for 44 days and give the research team access to the phone GPS data; 7) have smoked ≥ 100 cigarettes in their lives and currently smoke at least 1 cigarette per day on 3 or more days of the week (full trial: smoke at least 3 cigarettes per day on 5 or more days of the week); 8) are planning to quit smoking within the next 30 days.

B. Exclusion Criteria:

There are no additional exclusion criteria for participants that meet inclusion criteria.

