data collected in the initial 14 days of EMA monitoring, intervention messages will be delivered during time-periods and at high-risk locations for smoking. In the intervention phase, participants will be prompted to complete 3 geofence-triggered EMAs per day for a total of 30 days. Each EMA will be followed by an intervention message and the type of message (CBT, Mindfulness/ACT, control) will be randomly selected at each time point (within-subject randomization; see Figure). Each intervention message will also be tailored to situational factors from the EMA-pre data. Message tailoring will focus on two key situational triggers stemming from our conceptual framework: 1. Stress (high/low) and 2. Presence of other smokers (yes/no). For each situation, characterized by a combination of these 4 possible characteristics, several messages will be placed in separate message bins (4 bins for each CBT and Mindfulness/ACT messages, for a total of 8 bins). Control messages will thank participants for completing an assessment. Proximate outcomes will be assessed 15 minutes after message delivery and include urge levels, smoking or other tobacco product use since EMA-pre survey, affect, stress, and an evaluation of the last message (e.g., perceived usefulness of message, completion of suggested activity/intervention). In addition, participants will continue completing one brief retrospective EMA each morning. Just like the training phase, this retrospective EMA will assess cigarette and other tobacco product use, alcohol, cannabis, and drug use. Before we will embark on the full micro-randomized trial with N=80 participants, we will first conduct a brief pilot with N=10 participants to assess system functionality with current smartphones and operating systems.

[figure not shown]

Figure: Flow-chart for delivery of each intervention message in the micro-randomized trial group

Built-in parallel-group RCT – EMA-only control group (N=80)

[figure not shown]

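### Is it unfair to Mindfulness/ACT that the Aim 1 comparison with CBT has a written model only for urge?

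*Combined protocol and SAP*

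**What the plan says.** Section V.C.4, Analytical strategy Aim 1, names one outcome with a model: the EMA-post urge rating, adjusted for the EMA-pre rating, analysed by centered and weighted least squares with message type as the main predictor. It then says the trial will "test differences in efficacy between CBT versus Mindfulness/ACT", and gives that comparison no outcome of its own.

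Section I introduces CBT as a source of coping strategies for urges. It says Mindfulness and ACT "offer a different approach, which teaches smokers psychological flexibility through accepting negative experiences". The baseline survey description in Section V.C.1 counts urges among the negative states that the Avoidance and Inflexibility Scale asks about.

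Under Aim 1, Section I frames the three-way comparison as one of efficacy for lowering urge 15 minutes after the message. The next sentence reads: "Secondary outcomes include smoking or other tobacco use (including e-cigarettes), affect, and stress". Section V.C.1 (Intervention phase) lists what the EMA-post survey collects: "urge levels, smoking or other tobacco product use since EMA-pre survey, affect, stress, and an evaluation of the last message".

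Under Aim 2, Section I adds: "Post-hoc dose-response analyses investigate the long-term efficacy of CBT or Mindfulness/ACT messages on smoking behavior".

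**The concern.** If acceptance means letting the urge be present without acting on it, a participant who does that and does not smoke has used a Mindfulness/ACT message as intended, yet the urge rating shows no effect. CBT messages aim at the urge itself. A head-to-head test on urge could then report CBT as more efficacious although both types prevented the same amount of smoking.

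The studies cited in Section III.B seem to point the same way. For Aim 1 the plan cites a study in which "playing Tetris (analogous to a CBT distraction technique) decreased substance use urges", while the Aim 2 sample size rests on "findings from a recent app-based mindfulness meditation trial for smoking reduction", where the effect was on cigarettes per day.

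Aim 3 uses similar models to ask which message types help more in co-use situations, and its results are meant to inform later adaptive interventions. A ranking on urge alone could influence which type is delivered next.

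**Working it through.** **1. Which outcomes belong to the comparison.** Section I (Aim 1) names CBT, Mindfulness/ACT and control, ties efficacy to urge at 15 minutes, and then declares smoking a secondary outcome. Section V.C.1 collects urge and smoking in the same survey, after the same randomised message. Section V.C.4 repeats only the primary outcome. Read together, the sections give a primary contrast on urge and a secondary one on smoking, with no model written for the second.

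**2. The urge contrast.** Inputs from Section III.B: 80 people, 3 messages a day, 30 days, 75% compliance, probability 1/3 per type, d = 0.1, power 0.80, alpha 0.05.
- Observations: 80 × 3 × 30 = 7,200, as the plan states.
- Observed windows per type: 7,200 × 0.75 / 3 = 1,800.
- Simple check (constant effect, independent windows): SE = √(2/1,800) = 0.033 SD, and power at 0.1 SD = Φ(0.1/0.033 − 1.96) = Φ(1.04) = 0.85.
- A micro-randomized-trial calculation with a quadratic effect peaking at day 20 gives 0.82 to 0.87 for one type against the rest. It gives 0.70 to 0.75 for a pair of types, using two-thirds of the occasions. Both assume an initial effect of 0 to 0.05 SD. The first range also allows compliance to change by 0 to −1 point a day; the second holds it at 75%.
- The stated 0.80 lies among these figures. The plan does not say whether it refers to a pairwise contrast.
- Taking 0.80 as given, an F test on 1 and 76 degrees of freedom needs a noncentrality of 8.05. Scaling by (d/0.1)² gives power 0.29 at 0.05 SD and 0.99 at 0.15 SD.

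These are probabilities of detecting a real difference in urge. They are not error rates for the hypothesis that Aim 1 states.

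**3. The smoking contrast.** Half-width of the 95% interval = 1.96 × √(2p(1 − p)/1,800). The documents do not give the window smoking rate p, so a range is shown.

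| Assumed p | Half-width (points) | If clustering doubles the variance |
|---|---|---|
| 5% | 1.4 | 2.0 |
| 10% | 2.0 | 2.8 |
| 20% | 2.6 | 3.7 |

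At p = 10% the SE is 1.0 point. A true difference of 1.5 points between the types would be detected with probability Φ(1.5/1.0 − 1.96) = 0.32, or 0.19 with doubled variance. The contrast can be estimated usefully, but a null result would not show that the types are equal.

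**4. The other measures.** The Avoidance and Inflexibility Scale and FIT-60 are taken per person at baseline and follow-up. Each intervention participant is randomised among all types, so these scales cannot compare types.

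Dose-response cannot rank the types either:
- With 90 messages, the SD of the CBT-minus-ACT count is √(90 × 2/3) = 7.7.
- The correlation detectable with 80 people at 80% power is tanh(2.80/√77) = 0.309.
- All-CBT against all-ACT over 60 active messages is 120 units, or 120/7.7 = 15.5 SD of the count. Detectable difference: 15.5 × 0.309 = 4.8 SD of cigarettes per day.
- With 75% delivered it is 13.4 × 0.309 = 4.1 SD.
- At a true difference of 0.651 SD, the effect assumed for Aim 2, power is about 0.07.

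The plan's wording, however, is CBT or Mindfulness/ACT. It does not promise a contest between them.

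**The case for a change.** The strongest case for a change is that efficacy is a broad word, that the plan itself gives the two message types different mechanisms, and that the only type comparison with a written model uses the outcome nearer to the CBT mechanism. No acceptance item is collected at 15 minutes, and the scales and dose-response analysis cannot fill that gap (step 4). Naming window smoking as a second outcome of the contrast would cost a few sentences and one model.

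Part of this stands. Section V.C.4 could have repeated that the contrast extends to smoking since EMA-pre, and a report that calls one type better should name the outcome it rests on.

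The rest is weaker:
- Section II gives a reason for a common urge target that applies to both types: it ranks urges as the leading trigger and says smoking becomes much more likely as they strengthen.
- Section I speaks of accepting negative experiences. That this means leaving urges unchanged is an inference from a trait scale, whereas the plan expects both types to lower urge.
- The apparent split in the cited evidence is one study per aim, each cited for that aim's own outcome. Neither citation says what happened on the other outcome.
- An extra willingness item would lengthen up to three surveys a day, which Section V.C.1 tries to keep short.
- Making smoking a co-equal test would raise multiplicity. Splitting alpha to 0.025 lowers 0.80 to about 0.71.

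**Conclusion.** No change is needed. Followed as written, the plan yields a valid contrast on urge, which is how Aim 1 defines efficacy, and a declared secondary comparison on smoking from the same survey. The missing model statement, in a section whose template asks only for a short analysis plan, is a gap that an analyst fills by applying the named method to the secondary outcome and reporting the difference with its interval.

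The scenario behind the concern needs Mindfulness/ACT messages to leave urge about 0.1 SD higher than CBT messages while preventing equal smoking. The documents neither state nor support that figure. Even then, the 0.80 chance of a significant urge difference would reflect a true difference in urge, and the smoking estimate beside it would guard against reading it as a difference in smoking. How closely it would do so depends on the unknown window smoking rate: from 1.4 to 3.7 points either way over the range shown. Aim 3 is exploratory, and no rule in the plan selects a message type from this contrast.
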